### Simple Reaction Time

A repeated measures mixed-model design will be employed. A total of up to three groups (Device vs. no device vs concussion) will be examined using a 3 x 2 (group by time point; pre-season vs. post-season) ANOVA.

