This study will investigate the effectiveness of this device in high school athletes playing a collision sport such as football. The use of helmets during such a high-risk sport will allow for collision measurement devices to be embedded in the helmet and will not affect play or fit of equipment. Athletes participating in this study will be randomly assigned to one of two groups: 1) Device wearing during the season or 2) Non-device wearing during the season. By the nature of the sport selected, it is likely this pilot study will primarily include males, however if any female meets inclusion criteria on the team selected, she will be included in this investigation. The helmets of all participants will be outfitted with an accelerometer which will measure the magnitude of every impact to the head sustained by the athlete. Effectiveness of the device will be determined via differences in longitudinal brain imaging and functional testing following competitive football participation. A subset of athletes who report a diagnosed concussion will also receive additional brain neuroanatomical and neurophysiological testing within a week following the diagnosed concussive event. At each of these time points participants will also undergo various neurocognitive assessments outlined below.

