**(6) SELECTION & RECRUITMENT OF PARTICIPANTS:**

The purpose of the present study is to generate pilot data for effect size estimation and power analysis for future study. The group size proposed in the aims was determined empirically based on previous neuroimaging studies and study designs reported in the literature. The sample size proposed in this pilot study will not warrant extensive statistical analysis to test the listed hypothesis. This study is expected to lead to an accurate estimate of effect size and variability so that future studies can be designed more rigorously.

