We will recruit up to 60 study participants. The participants (age 14-19 years old) will be recruited from a local school district and local sports clubs and teams. Participants will be recruited using a top-down approach. We have gained the consent and the cooperation of the school district administrations. Presentations and letters from the research team will be given to each participating school to detail the participation requirements and study risks. The high-risk sports which utilize helmets during competition will allow for measurement devices to be embedded in the headgear and will not affect play or fit of equipment. By the nature of the sports selected, it is likely this study will primarily include males, however if any female meets inclusion criteria on the team selected, she will be included in the investigation. Questions regarding participation will be answered during the presentations or through e-mail or phone. Participants will be contacted via telephone to further explain the study, answer any additional questions and to enroll them in the study. The participants and parents/guardians who voluntarily agree to participate will be scheduled to complete the pre-participation testing. The participant and parent/guardian will read and sign the "Consent to Participate in a Research Study" form, approved by the Institutional Review Board of Cincinnati Children's Hospital. If the participant and parent/guardian does not read or sign the form, they will not participate in the study. Once the potential study participants/school teams are identified, they will be allocated to one of two groups: 1) Device wearing during the season or 2) Non-device wearing during the season. This research does not mandate that the participant maintains participation in their sport. The desire to participate in the sporting event is an independent, personal decision separate from the decision to enter into this study. If any athlete chooses to stop participation in the sporting activity then they will also be withdrawn from the study, due to no longer meeting inclusion criteria.

Inclusionary criteria include:

- Normal healthy volunteer
- Able to provide written consent

- Must be 14 years or older and a participant on varsity level high school football team

Exclusionary criteria include:

- Unable to provide written consent
- History of neurological deficits, previous cerebral infarction, or severe head trauma as indicated through pre-season screening:

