### **Injury Surveillance**

*Device and Compliance Acceptance:* The study coordinator will be responsible for providing the appropriate intervention (device or no-device) to each team based on their random

be reported according to criteria outlined in recent multi-investigator consensus documents (McCrary, 2013). The incidence of concussion will be calculated in this study using cases identified through two primary mechanisms: 1) Monitoring of concussion injuries and time missed from planned physical activity by the AT for each team, and 2) weekly inquiries to each coach by the Study Coordinator as to whether any participants are missing time from activity due to concussion. This dual query approach enables the Study Coordinator to cross check the injury and exposure data collected to improve the accuracy of the data. The data secured from the coach regarding each athlete's participation in individual practices and games combined with accelerometer exposure to impacts allows the research team to capture robust individual athlete exposures rather than just combined team exposures.

The athletic trainer will evaluate any athlete for whom a concussive event has been observed (within 24 hours). If criteria for concussive sequelae are not met, the athlete is cleared for return to play. In the event of a positive concussion evaluation by the AT, an MD will perform a second evaluation. Should the MD concur with the AT on a positive evaluation, a diagnosis of isolated concussion is made and the athlete is removed from play and participant is referred for to a post-concussion evaluation. The diagnosing physician will be blinded to the experimental treatment of the study participants.

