**Statistical analyses.** - Statistical analysis of outcomes measures will be done using SAS®, version 9.3 (SAS Institute, Cary, NC) and SPSS statistical software (SPSS Inc, Chicago IL). Comparisons between the testing conditions (collar vs. no collar) will be made using Analysis of Covariance, in order to control for time (pre vs post season) and condition (collar versus no collar). We will also conduct correlation analysis to test the association between imaging biomarkers (as described above) with the results obtained from the impact surveillance. The collision indices,

including total number of collisions, number of collisions from front, back, left, right, top, bottom, G force, and timing of each collision will all be recorded and tested in the analysis. Secondary analysis to compare the intervention with no intervention and calculate the rates would involve a Poisson model, using an offset to account for the playing time and exposure to concussive impact for each of the study participants. We will calculate the rate and the associated 95% confidence interval. SAS®, PROC GENMOD will be used for analysis, which allows us to account for the fixed and random effects, use the appropriate link function, and the offset for amount of playing time exposure.

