### Oculomotor Measures

Oculomotor control performance will also be compared using a 3 × 2 mixed-model ANOVA for each of the dependent variables. For smooth pursuit tracking performance, mean eye peak velocity and tracking lag will be submitted to separate 3 (group) × 2 (session) × 2 (random vs. sinusoidal task condition) mixed-model ANOVA.

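### The reaction-time and oculomotor models make concussion a third group, so their device contrast would leave out concussed athletes, and its link to the two-arm ANCOVA is not stated

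*Combined protocol and SAP*

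**What the plan says.** The Abstract sets up two groups: "Athletes participating in this study will be randomly assigned to one of two groups", device or no device. Concussion is not an assigned group. Under Injury Surveillance in section (8), it is diagnosed in season by the athletic trainer and then a physician.

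Section (9) contains two kinds of group comparison:

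- **Statistical analyses paragraph (general):** "Comparisons between the testing conditions (collar vs. no collar) will be made using Analysis of Covariance". It has two groups and names neither the reaction-time nor the oculomotor battery.
- **Simple Reaction Time:** "A total of up to three groups (Device vs. no device vs concussion) will be examined", in a group by time (pre-season, post-season) ANOVA.
- **Oculomotor Measures:** "Oculomotor control performance will also be compared using a 3 × 2 mixed-model ANOVA for each of the dependent variables". Smooth pursuit gets a further model with a three-level group factor, session and task condition. The three levels are not named again; the wording carries them over from the reaction-time paragraph.

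No section says who belongs to the concussion group, whether it pools both arms, or whether these ANOVAs replace or supplement the ANCOVA. On what the study should deliver, section (6) says: "This study is expected to lead to an accurate estimate of effect size and variability".

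**The concern.** Concussion occurs after assignment, and the device is meant to affect it. Using it to define a comparison group conditions the device contrast on a post-assignment outcome. This has two consequences. Any benefit that arises because fewer collar wearers are concussed drops out of the contrast. And if concussion risk differs between arms, the athletes left in each arm are selected differently and may no longer be comparable.

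The stated purpose in section (2) is change over the season in football players with and without the device, with no restriction to those who escaped concussion. Because the pilot is meant to supply an effect size for later studies, what that estimate means matters. As written, two contrasts with different meanings could be produced for the same measures, and the plan does not say which one is the device effect.

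**Working it through.** **1. Structure.** The plan gives no concussion rate, effect size or SD, so there is no stated figure to reproduce. The first step is logical. Group is the between-athlete factor and time is the repeated one, and the levels of a between-athlete factor are mutually exclusive. A concussed athlete in the third level is therefore absent from the assigned arm. The only alternative is to count that athlete twice, which breaks the independence between groups that the model needs.

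**2. Size of the difference between the two contrasts.** Everything in this step is assumed. The change score has SD 1, with positive values worse. The collar halves the concussion risk and has no other effect. Concussion worsens change by s = 0.5 or 1.0 SD. Write p0 and p1 for the risk without and with the device, z0 and z1 for the matching normal cut-offs, and r1 and r2 for the correlations of latent vulnerability with concussion liability and with change.

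- As assigned: difference = −s × (p0 − p1)
- Non-concussed only: difference = r1 × r2 × [φ(z0)/(1 − p0) − φ(z1)/(1 − p1)]

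The bracket equals 0.0486, 0.0864 and 0.1550 for the three risk pairs below. Differences are device minus no device, so negative values favour the collar.

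| Risk, no device vs device | As assigned, s = 0.5 / 1.0 | Non-concussed, (r1, r2) = (0, 0) / (0.3, 0.3) / (0.5, 0.5) / (0.7, 0.6) |
|---|---|---|
| 5% vs 2.5% | −0.0125 / −0.025 | 0 / +0.004 / +0.012 / +0.020 |
| 10% vs 5% | −0.025 / −0.050 | 0 / +0.008 / +0.022 / +0.036 |
| 20% vs 10% | −0.050 / −0.100 | 0 / +0.014 / +0.039 / +0.065 |

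The smallest gap is 0.0125 SD (5% risk, s = 0.5, no selection). The largest is 0.100 + 0.065 = 0.165 SD (20% risk, s = 1.0, strong selection). Simulation with 4,000,000 athletes per arm agreed with the formulas to within about 0.002. A separate simulation with equal risks of 10% in both arms gave a difference of essentially zero for both contrasts.

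**3. Sampling error.** Section (6) gives up to 60 athletes. Assume 30 per arm and individual allocation. The standard error is √(1/n1 + 1/n0), with the expected numbers of non-concussed athletes:

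- 29.25 vs 28.5: 0.263 SD
- 28.5 vs 27: 0.269 SD
- 27 vs 24: 0.281 SD

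Some wording points to allocation by team (section (6): "Once the potential study participants/school teams are identified, they will be allocated to one of two groups"), which would raise these values. With 27 vs 24 athletes, one or two teams per arm and an intraclass correlation of 0.01 to 0.10 (all assumed), the range is 0.297 to 0.520 SD. The gap in step 2 is below the standard error in every case.

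**4. Precision lost by moving athletes out of the arms.** At equal concussion rates of 5%, 10% and 20%, 60 × rate = 3, 6 and 12 athletes move to the third level, leaving 28.5, 27 and 24 per arm. The difference detectable with 80% power at two-sided 0.05 is (1.960 + 0.842) × √(2/n). It rises from 0.72 SD at 30 per arm to 0.74, 0.76 and 0.81 SD, a modest loss.

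**The case against.** The strongest reply is that the as-assigned contrast is already planned. The ANCOVA sentence is a general rule for outcome measures; it names no battery at all, so its silence on these two means little. On that reading, the three-group models only add a comparison with concussed athletes, for which section (8) gives a reason: the repeated battery lets typical and concussed data be compared. This partly stands. The ANCOVA may cover these measures, but the only text specific to them prescribes the three-group model, and nothing says which analysis yields the device effect.

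Second, the exclusion of concussed athletes is inferred, and the reaction-time paragraph allows for fewer than three groups. It is indeed an inference, but the only other reading counts athletes twice. The factor reduces to two levels with certainty only if nobody is concussed, whereas section (12) lists concussion among the injuries expected.

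Third, concussion prevention is not lost from the study. Incidence is calculated, rates are compared by a Poisson model, and time unfit to play is an endpoint. That is correct, and it confines the point to one contrast in two batteries.

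Fourth, the shift is below sampling error, and section (6) describes a pilot too small for extensive testing. Both are correct. The 1.0 SD input is also a strong assumption, since section (8) has concussed athletes re-evaluated until they return to baseline. These facts limit the weight of the point but do not remove the ambiguity.

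**Conclusion.** The concern holds, at minor severity. Followed as written, the reaction-time and oculomotor models give a device contrast restricted to athletes who were not concussed, and the plan does not say how this relates to the two-arm ANCOVA. Under the assumptions shown, the two contrasts differ by about 0.01 to 0.17 SD, against a standard error of 0.26 to 0.28 SD with individual allocation and more with allocation by team. In those scenarios the restricted contrast is zero or slightly adverse even though the collar helps. The issue is what the estimate means; the numerical shift would not be visible in a study of this size.

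Confidence is medium, because group membership is inferred from the model's structure and the risks, effects and correlations are all assumed. The issue disappears if no athlete is concussed. Imaging, EEG and the Poisson model are not affected.

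**What to change.** In the Simple Reaction Time and Oculomotor Measures paragraphs of section (9):

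1. Estimate the device effect with a two-level group factor (device, no device) by time, and by task condition for smooth pursuit. Keep every athlete with post-season data in the assigned arm, concussed or not.
2. State that this is the same comparison as the ANCOVA in the Statistical analyses paragraph, or say how it differs.
3. Keep any three-group or concussed-athlete analysis as secondary and descriptive. Define who belongs to the concussion group, report it by arm, and do not read its omnibus test as a device effect.
4. As a supporting item, tabulate by arm, with reasons, the athletes without post-season data. Section (6) states "If any athlete chooses to stop participation in the sporting activity then they will also be withdrawn from the study", and section (8) repeats this for athletes who stop after a concussion.

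The cost is two or three sentences and one table of counts, with no new data collection. The change cannot recover post-season values for withdrawn athletes, which is why the counts are needed.

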Post-concussion and post season testing consists of the same battery of tests as performed for pre-season testing, which allows for direct comparison between typical and concussed data. In addition, concussed athletes will complete the Post-Concussion Symptom Inventory (PCSI) questionnaire at the beginning of the testing session and repeated at the conclusion of this session. Additional neurologic testing is done on athletes with confirmed or suspected concussion to narrow down neuro-systems involved. Concussion evaluations will be repeated as needed until the MD is satisfied that the athlete has fully recovered from the concussion. This includes a return to baseline at rest, no exam abnormalities, and baseline symptoms with sports-specific exertion; whereupon the athlete will be cleared for return to activity. The amount of time the athlete was considered unfit to play will also be considered as one of the endpoints of this study. If any athlete chooses to stop participation in the sporting activity following a concussion then they will also be withdrawn from the study, due to no longer meeting inclusion criteria.

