**Statistical considerations.** The data analysis will begin with a review of descriptive statistics for all major variables and all major subgroupings of variables in the data set. For the inferential methods, we will use a number of different generalized linear modeling techniques, including linear regression models. All analyses will be conducted using SAS® version 9.3 (SAS Inst, Cary, NC), or Mplus (Muthén, 2007). Initial analyses will be undertaken to inspect data for errors, inconsistencies, and incomplete information. This will include examining the data with simple frequency tables and dot plots for univariate data and scatter plots and multi-way dot plots for bivariate and multivariate data. Data anomalies that cannot be resolved by the Biostatistical/data management team will be sent as queries via email to the project investigator for clarification and/or correction. During the verification process, outlying values will be corrected if necessary. Incomplete information will be corrected and the project investigator will receive updates. To summarize bivariate relationships among predictors and between predictors and outcomes, Chi-square of Fisher's exact test or Spearman's rank correlation coefficient, will be used, as appropriate. For reporting inferential statistics, such as differences in rates or means, 95 percent confidence intervals will be used extensively to quantify degree of clinical efficacy. Unless otherwise stated, statistical tests are considered two-sided and a .05 significance level is used. All models will be adjusted for potential independent predictor variables but will be limited to the number of predictors we can fit in a regression model while maintaining a valid and reliable model. Candidate predictors include amount of playing time, amount of practice time, previous mTBI, weight, age and height. Collinearity will be examined. Linearity assumptions will be checked and transformations examined. In those cases, a log transformation, polynomial terms, or restricted cubic splines will likely be used to relax the assumption of linearity in the regression models. We will remove the nonlinear terms or transformation only if the nonlinear test is non-significant with a  $p \geq .10$ . Additionally, overly-influential observations and distributional assumptions will be checked. Models will be interpreted graphically, predicted values will be examined, and appropriate significance tests will be utilized.

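### Reaction-time and oculomotor outcomes are compared by change from pre-season; adjusting for the pre-season score already collected would give a somewhat narrower interval at almost no cost

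*Combined protocol and SAP*

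**What the plan says.** Section (9), Simple Reaction Time, describes "A total of up to three groups (Device vs. no device vs concussion" (the bracket closes there) and says these "will be examined using a 3 x 2 (group by time point; pre-season vs. post-season) ANOVA". Oculomotor Measures follows suit: "Oculomotor control performance will also be compared using a 3 × 2 mixed-model ANOVA for each of the dependent variables". For smooth pursuit a third factor, task condition, is added.

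The pre-season scores exist. Section (8), Injury Surveillance, states: "Post-concussion and post season testing consists of the same battery of tests as performed for pre-season testing".

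Two other paragraphs of section (9) bear on adjustment. Statistical analyses says that collar comparisons will be "made using Analysis of Covariance, in order to control for time (pre vs post season) and condition (collar versus no collar" (again the bracket closes there). Statistical considerations says that models will be adjusted for predictors: "Candidate predictors include amount of playing time, amount of practice time, previous mTBI, weight, age and height". Neither names the pre-season value of the outcome.

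On size and purpose, section (6) says "We will recruit up to 60 study participants" and gives the aim of the pilot as accurate estimation of effect size and variability for later studies.

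**The concern.** In the planned ANOVA the pre-season score is one of two levels of the outcome. The interaction therefore compares post-minus-pre change between groups, which amounts to fixing the slope of post-season on pre-season score at 1. When the true slope is lower, as it is with equal SDs and any correlation below 1, change carries extra noise from the pre-season measurement. A model that estimates the slope removes that noise.

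The measures affected are two reaction-time measures (visual and auditory) and nine listed oculomotor measures: five for reflexive saccades, two for self-paced saccades and two for smooth pursuit. At stake is the width of the intervals around the effect estimates that the pilot is meant to hand on to a later trial.

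**Working it through.** The plan gives no power, effect size, SD or correlation for these outcomes, so there is no figure to reproduce.

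**Inputs from the documents.** At most 60 athletes (section (6)); two planned time points; two-sided 0.05 level and 95% intervals (section (9), Statistical considerations: "statistical tests are considered two-sided and a .05 significance level is used").

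**Assumptions.** Individual randomisation; 30 per arm (the allocation ratio is not stated) with no dropout; SD = 1 at both times; r from 0.5 to 0.9.

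**Step 1: is the interaction a change-score test?** In one simulated data set with three groups (26, 26 and 8 athletes) and two times, the group-by-time F and the one-way ANOVA F on change were both 0.90991. They are the same test.

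**Step 2: variances.** Write b for the within-arm slope of post-season on pre-season score. Change equals the regression residual plus (b − 1) times the pre-season score, so its variance is the residual variance plus (1 − b)² times the pre-season variance. In large samples it cannot be smaller than the residual variance. With equal SDs of 1, b = r and:

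- change: V = (1 − r)² + (1 − r²) = 2(1 − r)
- adjusted: V = 1 − r²
- ratio, adjusted to change: (1 + r)/2

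**Step 3: cost of estimating the slope.** With n = 30 per arm the adjusted variance is multiplied by 1 + 1/(2n − 4) = 1 + 1/56, and the degrees of freedom fall from 58 to 57.

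**Step 4: 95% half-width** = t × √(V × 2/n). At r = 0.5, change gives 2.002 × √(1 × 2/30) = 0.517, and adjusted gives 2.002 × √(0.75 × 57/56 × 2/30) = 0.452.

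| r | Variance ratio, slope cost included | Half-width, change (SD) | Half-width, adjusted (SD) | Narrower by |
|---|---|---|---|---|
| 0.5 | 0.763 | 0.517 | 0.452 | 13% |
| 0.7 | 0.865 | 0.400 | 0.373 | 7% |
| 0.8 | 0.916 | 0.327 | 0.313 | 4% |
| 0.9 | 0.967 | 0.231 | 0.227 | 2% |

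**Step 5: check by simulation.** In 20,000 trials at each r, the variance ratio was 0.77, 0.86 and 0.96 at r = 0.5, 0.7 and 0.9, in line with the formula.

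**Step 6: limits of the gain.** At r = 0.5 the change analysis is no more precise than ignoring the pre-season score altogether (half-width 0.517 SD either way). At the other end, (1 + r)/2 × 57/56 = 1 gives r = 0.965; above that, adjustment no longer pays at this sample size.

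**The case against.** The planned ANOVA is not wrong. A reader might infer that it gives a biased or invalid device comparison. Under individual randomisation it does not, and the point is one of precision only.

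A reader might also fear that the group main effect, which averages pre- and post-season scores, would be taken as the device effect and so dilute it. The plan does not say so. Its group-by-time wording and the stated purpose in section (2), longitudinal change, both point to the interaction.

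It can be argued that the ANCOVA in the Statistical analyses paragraph already covers the collar comparison for every outcome, and that the three-group ANOVA is additional. The text allows that reading, and the predictor list is open-ended. But the ANCOVA is described as controlling for time and condition, which are design factors. Even on this reading the covariate is still unnamed, so that paragraph needs the same sentence.

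The strongest objection concerns allocation. Section (1) randomises athletes, whereas section (6) speaks of participants or school teams, and Injury Surveillance in section (8) has the intervention given to each team (that sentence is broken off in the text available). If teams are allocated, pre-season means may differ between arms and the two methods can estimate different things. Suppose, as an illustration, a stable gap of 0.3 SD between arms and no device effect. Change scores give 0. Adjustment gives (1 − r) × 0.3, which is 0.15 SD at r = 0.5 and 0.09 SD at r = 0.7. This objection stands as a condition on the recommendation.

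The gain is also small when r is high, and section (6) says that the sample will not support extensive hypothesis testing. Both are fair, which is why the size is given here as interval width rather than power.

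**Conclusion.** The point holds as a modest matter of efficiency. For these eleven measures, the planned device versus no-device test is a valid change-score test that leaves unused some of the information in the pre-season scores. With individual randomisation, equal SDs and about 30 per arm, adjustment would narrow the 95% interval by about 13% at r = 0.5, falling to 2% at r = 0.9. The SDs, the per-arm size and r are all assumed.

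The documents do not support calling this a large loss: r is unknown and no target effect is given. The advantage applies only to the randomised two-arm contrast. The concussion group forms after allocation, so neither method makes its comparison a randomised one.

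**What to change.** In Simple Reaction Time and Oculomotor Measures, and in matching words in the Statistical analyses paragraph:

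- Estimate the device versus no-device effect with a linear model of the post-season score on allocated arm and pre-season score. Report the adjusted difference with its 95% confidence interval.
- State that all athletes, including those who are concussed, are analysed in their allocated arm.
- For smooth pursuit, keep task condition as a within-athlete factor and use the matching pre-season score.
- Keep the three-group group-by-time ANOVA as a descriptive display.
- Reconcile sections (1), (6) and (8) on the unit of allocation. If teams were allocated, account for team in the model and show the change-score estimate as a sensitivity analysis.

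The cost is plan wording, one degree of freedom per model and a little more analysis work. No new data are needed.
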